2.3 Assessment and management of risk

The ISWT and CPET require physical effort and exertion. In rare cases these tests can cause myocardial infarction, cardiac arrhythmia, orthopaedic injury or, in exceptional circumstances, death. A specialist physiologist will assess each participant's fitness to carry out these tests beforehand. If a participant reports any chest pain or severe discomfort then the test will be stopped.

3 OBJECTIVES AND OUTCOME MEASURES/ENDPOINTS

3.1 Primary objective

To assess the relationship between VO_2 peak and ISWT distance and to determine how similar it is to a linear relationship from other data collected in a previous study with the following relationship:

$$\text{VO}_2 \text{ peak} = 10.02 + (0.01575 \times \text{ISWT distance})$$

3.2 Primary endpoint/outcome

VO₂ peak

4 TRIAL DESIGN

This is a basic science study involving procedures with human participants

5 STUDY SETTING

This study will be conducted at University Hospital, Coventry. All visits will take place in the Respiratory Physiology and Sleep Department, located within the Outpatients area of the hospital.

6 ELIGIBILITY CRITERIA

We will recruit a minimum of 43 participants to this study. In each case, the following inclusion and exclusion criteria will apply.

6.1 Inclusion criteria

- A diagnosis of IPF confirmed by a multidisciplinary team
- Over 16 years of age

6.2 Exclusion criteria

- Patients absolutely contraindicated for ISWT or ICET. Contraindications are summarised in table one. Where a patient has a relative contraindication, the test will be discussed with their medical team and a decision made as to whether or not to proceed.
- Inability to undertake ISWT or CPET
- Inability to walk without a walking aid such as a stick or frame
- Inability to give informed consent for testing

Absolute contraindications	Relative contraindications
Acute myocardial infarction (3–5 days) Unstable angina Uncontrolled arrhythmias causing symptoms or haemodynamic compromise Syncope Active endocarditis Acute myocarditis or pericarditis Symptomatic severe aortic stenosis Uncontrolled heart failure Acute pulmonary embolus or pulmonary infarction Thrombosis of lower extremities Suspected dissecting aneurysm Uncontrolled asthma Pulmonary oedema Room air SpO ₂ at rest ≤ 85% Acute respiratory failure Acute non-cardiopulmonary disorder that may affect exercise performance or be aggravated by exercise (i.e. infection, renal failure, thyrotoxicosis) Mental impairment leading to inability to cooperate	Left main coronary stenosis or its equivalent Moderate stenotic valvular heart disease Severe untreated arterial hypertension at rest (200 mmHg systolic, 120 mmHg diastolic) Tachyarrhythmias or bradyarrhythmias High-degree atrioventricular block Hypertrophic cardiomyopathy Significant pulmonary hypertension Advanced or complicated pregnancy Electrolyte abnormalities Orthopaedic impairment that prevents walking

7 TRIAL PROCEDURES

7.1 Recruitment

7.1.1 Patient identification

Patients known to have IPF and included in departmental IPF database will be sent a letter inviting them to take part in this research project. The letter will include a description of the study and will ask anybody

who is interested in taking part to contact [name] by phone, email or letter. Potential participants who are interested in taking part will be given information about the study including a written document and then at least 48 hours to decide whether or not to take part.

7.1.2 Screening

Only patients with a confirmed diagnosis of IPF will be asked to take part in the study. All participants will then be asked to fill in a participant questionnaire which will ask participants if they are taking part in any other research trials at the moment, about any other medical conditions which could contraindicate their taking part and whether or not they require a walking aid.

7.2 Consent

This study will obtain consent from adult participants only. Only patients deemed fit to give informed consent will be included in the study. All patients will be given a verbal outline of the study, given an information sheet to read and time to ask any questions that they might have about the research and their involvement. Potential participants still interested in taking part will be given a minimum of two days to decide whether or not they would like to take part. After this time a member of the research team will call the patient. There will be time for questions to be answered. If they would like to take part then they will be invited into University Hospital to give their informed consent by signing the consent form.

7.3 Baseline data

Any comorbidities will be asked for on the participant information sheet. No other baseline data will be required before visit one.

7.4 Trial assessments

At one visit participants will be asked to undertake an ISWT; walking 10 m between cones at an increasing speed dictated by a standardised audiotape. The ISWT will be performed according to the standardised protocol set out by Singh et al. (1992) and our department protocol. At the other visit participants will undertake an Incremental Cycle Ergometry Test (ICET). The ICET will be performed on a static exercise bike following the department protocol. After each of these exercise tests a capillary blood sample will be taken from the participant's earlobe by a trained member of staff following department protocol. The blood sample will be analysed and oxygen pressure will be recorded. Both visits will be in the Respiratory Physiology and Sleep Department at University Hospital, Coventry.

7.5 Statistical analysis

The data collected in this study will be combined with data from the previous study in our department and distinguished by a study indicator. The similarity between the two datasets will be tested using a series of linear regression models. The value of PO₂, measured in capillary blood, after ISWT and after CPET will be compared using a paired t-test. All analyses will be performed in SPSS statistical software. We do not anticipate missing data. Should a participant withdraw from the study then none of the identifiable data that they generated will be used.

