1. INTRODUCTION

Idiopathic pulmonary fibrosis (IPF) is a chronic and fatal lung disease. As IPF progresses, patients become increasingly breathless with reduced exercise capacity and quality of life. Average life expectancy is three years from diagnosis but IPF progresses at different rates in different people. In 2012 the British Lung Foundation estimated that 32,500 in the UK had IPF.

An accurate prognosis can help determine the most appropriate treatment option and allow patients and their families to make suitable plans. Currently, measurements made during resting lung function tests are used to predict prognosis. However, evidence suggests that measurements made during a cardiopulmonary exercise test (CPET), particularly peak oxygen consumption (VO_2 peak) are more sensitive predictors of survival. CPET is the gold standard for assessing IPF but has not been adopted in clinical practice.

The incremental shuttle walk test (ISWT) is quicker, cheaper and more widely available than CPET. This study builds on previous research from our department which showed a relationship between the distance walked in an ISWT and VO_2 peak during a CPET. We will identify any relationship between ISWT distance and VO_2 peak in a new cohort of patients and compare this with the relationship of the previous study. Patients will undertake both ISWT and CPET and the results will be compared. This study paves the way for a simple, standardised test to more accurately predict prognosis in IPF.

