1.3 Study population

This is a prospective study of patients with a diagnosis of IPF confirmed by a multi-disciplinary team. We aim to recruit a minimum of 43 patients to this study, all of whom will already be under the care of a Respiratory Consultant at University Hospitals Coventry and Warwickshire NHS Trust.

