1 RATIONALE

2.1 Aims and hypothesis

- To test the relationship between VO_2 peak and the distance walked in an ISWT
- To test the hypothesis that PO_2 is the same at the end of an ISWT and a CPET.

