2.2 Justification

This project tests a formula proposed by Fielding et al. (2015) to predict VO_2 peak during an ICET using distance walked in an ISWT. It will compare predicted VO_2 peak value with the actual value in a new cohort of patients with IPF. In addition, this study will test the relationship between PO_2 at the end of an ICET and at the end of an ISWT.

NICE recognises the importance of providing patients and their families with information when IPF is diagnosed and as the disease progresses (NICE, 2013b). Patients can be better informed about expectations of future symptoms and management, their treatment options and their life expectancy if more accurate prognostic tests are available.

This study paves the way for a relatively cheap and widely available incremental exercise test to be used to gather helpful information about a patient's prognosis. In the future, such a test could be recommended for making prognostic predictions in IPF.

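### Section 7.5 specifies no analysis of VO2 peak on ISWT distance in the new cohort alone; its only such analysis combines the new data with the study that produced the formula

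*Combined protocol and SAP*

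**What the plan says.** Section 7.5 is the only statistical section. Its plan for VO2 peak and ISWT distance is two sentences: "The data collected in this study will be combined with data from the previous study in our department and distinguished by a study indicator", and "The similarity between the two datasets will be tested using a series of linear regression models". It does not list the terms in the models. It names no regression on the new participants alone, no indicator-by-distance term, no confidence interval and no criterion for calling the datasets similar.

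Other sections describe work in the new cohort:

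- Section 1 (Introduction): "We will identify any relationship between ISWT distance and VO_2 peak in a new cohort of patients", to be compared with the relationship in the previous study.
- Section 1.1 (Background): the formula, derived by linear regression in the previous departmental study, is to be tested in a new cohort.
- Section 2.2 (Justification): "It will compare predicted VO_2 peak value with the actual value in a new cohort of patients with IPF".
- Section 2.1 (Aims and hypothesis), first aim: "To test the relationship between VO_2 peak and the distance walked in an ISWT".
- Section 3.1 (Primary objective) has two parts: assess the relationship, and "to determine how similar it is to a linear relationship from other data collected in a previous study".

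On size, section 1.3 (Study population) says "We aim to recruit a minimum of 43 patients to this study".

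**The concern.** The stated aim contains two questions. One is whether VO2 peak is related to ISWT distance in patients who played no part in deriving the formula. The other is whether that relationship resembles the earlier one. Section 7.5 addresses only the second, and does so in data that include the patients who generated the hypothesis.

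A series of regressions on combined data often runs as follows: test the study-by-distance term, drop it if it is not significant, and report the common slope. Nothing in 7.5 rules this out. The reported slope would then average old and new patients, and its p-value would partly restate the result of the previous departmental study. The new cohort was recruited to provide independent evidence, and that evidence might never be shown separately. A conclusion of similar and strongly related could be reached when the new patients alone do not show the relationship.

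**Working it through.** **What the documents supply.** New n = 43 (minimum) and old slope 0.01575 ml/kg/min per metre if VO2 peak is in the per-kilogram units used in section 1.1; the result does not depend on the unit. No derivation is given for 43, so there is no planned figure to reproduce.

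**What has to be assumed.** Old n of 20 to 43; old correlation r of 0.5 to 0.7; distance SD of 150 m in both cohorts; equal residual SD; two-sided 5% tests.

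**Step 1: residual SD implied by the old slope and r.** Residual SD = slope × SD(distance) × √(1/r² − 1), with 0.01575 × 150 = 2.3625.

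- r = 0.5: 2.3625 × 1.732 = 4.09
- r = 0.6: 2.3625 × 1.333 = 3.15
- r = 0.7: 2.3625 × 1.020 = 2.41

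**Step 2: models fitted to simulated trials** (2,000 or more per setting).

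- (a) distance plus study indicator, with a common slope;
- (b) the same plus indicator × distance;
- (c) distance in the 43 new patients only.

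**Step 3: each test taken alone, new slope zero.**

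- Common slope in (a) significant: 27% (old n = 20, r = 0.5) to 96% (old n = 43, r = 0.7).
- Interaction in (b) significant: 52-73% at r = 0.5 and 90-99% at r = 0.7.
- New cohort alone in (c) significant: about 5%, as it should be.

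The first line does not measure the risk by itself, because the interaction usually flags the difference in the settings where the common slope is most often significant.

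**Step 4: the joint event that matters.** The common slope is significant, the interaction is not, and the new cohort alone is not. Ranges are over old n = 20 to 43.

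| Old r | New slope zero | New slope 40% of old |
|---|---|---|
| 0.5 | 10-16% | 26-33% |
| 0.6 | 6-8% | 16-21% |
| 0.7 | 1-3% | 2-8% |

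Simulation error is about one percentage point: √(0.16 × 0.84 / 2,000) = 0.8 points at the top of the first column. A separate run of the same grid agreed within about that margin.

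**Step 5: how easily the common-slope branch is reached.** With a new slope half the old one, the interaction is significant in only 17-27% of trials at r = 0.5 and 40-61% at r = 0.7 (old n = 20 to 43). A non-significant between-study term is therefore weak evidence that the slopes agree.

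**Step 6: power of the new-cohort analysis.** If the new slope equals the old one, regression in the 43 alone is significant in about 94% of trials at r = 0.5 and about 100% at r = 0.7.

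**The case against.** The strongest reply is that 7.5 does not propose undifferentiated pooling. The study indicator is there so that the cohorts can be compared, the stated test is of similarity, and the primary objective of comparing the new relationship with the earlier line reasonably uses both datasets. If the series includes an indicator-by-distance term, the slope and intercept it gives for the new cohort are identical to those from regressing the 43 alone; only the residual variance is shared. Sections 1, 1.1 and 2.2 also make the new-cohort intent plain.

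Most of this stands, and it limits the point. A reader might infer that the plan offers the pooled slope as proof of aim 1, so that the old data would confirm it in 70-97% of trials even with no relationship in the new patients. The documents do not support that. Section 7.5 never says that the common slope or its p-value is evidence for aim 1. Those rates (old n = 43) also ignore the similarity test that 7.5 does name; once it is taken into account, the 96-97% setting falls to about 1%.

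A reader might also infer that forcing one residual variance on both studies makes the tests wrong. Nothing in the documents indicates different scatter, and both studies come from one department, so this is a possibility to check and not a demonstrated fault.

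What the reply does not supply is the missing analysis. The interaction term is not named, and the new-cohort intent stated elsewhere never becomes a specified analysis. A common-slope fit reported for aim 1 would comply with 7.5 as written.

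**Conclusion.** The point holds in a limited form. The statistical section does not deliver the new-cohort estimate that other sections promise, and its only VO2 peak-ISWT analysis includes the data that produced the formula. The consequence depends on a model form that 7.5 leaves open. If the series ends in a common-slope model, the misleading combination defined in step 4 occurs in about 1-16% of trials with a zero new slope and about 2-33% with a new slope 40% of the old. It is most frequent when the old correlation is weak and small when r is near 0.7. Old n, old r and distance SD are all assumptions; the sponsor holds the old data and can replace them with actual values. This should be changed before analysis, but it does not invalidate the design or the data collection.

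**What to change.** In section 7.5:

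1. State that the aim 1 analysis is the linear regression of VO2 peak on ISWT distance in the new participants only, reporting slope, intercept, r and residual SD with 95% confidence intervals.
2. Report alongside it, in the same participants, the predicted VO2 peak from the earlier formula against the observed value, as section 2.2 already intends.
3. Use the combined data only for the between-study contrast, with the indicator and indicator-by-distance terms both reported with confidence intervals.
4. State that the common slope and its p-value will not be cited as evidence for aim 1.

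Study-specific residual variances, or HC3 standard errors, may be added to the contrast as an optional sensitivity check.

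The cost is a few sentences and no new data. The new-cohort interval for the slope will be wider than the pooled one. With equal slopes, distance SD and residual SD in both studies, the ratio of standard errors is √((42 + 19)/42) = 1.2 for 20 old patients and √((42 + 42)/42) = 1.4 for 43.

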Current NICE guidelines (2013b) for IPF management recommend using resting measurements of spirometry and gas transfer to assess disease severity and likely prognosis. However, patients with IPF demonstrate significant exercise limitation due to impaired gas exchange and ventilation (Miki et al., 2003). Measurements made during exercise have been shown to be more sensitive to the changes in oxygen transfer associated with IPF than those made at rest (Ley et al. 2011). CPET is recognised as a gold standard test for IPF assessment but has not been routinely adopted in practice (Bonini and Fiorenzano, 2017).

A study of IPF by Kawut et al. (2005) showed that VO_2 peak in a maximal CPET was inversely proportional to a patient's risk of death. Similarly, Fell et al. (2009) found that a VO_2 peak of < 8.3 ml/kg/min in a CPET was associated with an increased risk of death in patients with IPF. Oxygen consumption during an incremental treadmill test and an ISWT increases similarly (Singh et al., 1994) and, because an ISWT is cheaper, quicker and easier to perform, the usefulness of measurements made during an ISWT should be evaluated in more detail.

Moloney et al. (2003) demonstrated a significant correlation between total distance walked in a corridor ISWT by patients with IPF and the VO_2 max measured during a shuttle walk test on a treadmill. In a previous study in our department the distance walked in an ISWT by patients diagnosed with IPF

ISWT vs CPET

correlated with the individual's VO_2 peak during an incremental cycle ergometry test (ICET) (Fielding et al., 2015). Linear regression was used to derive a formula which predicted VO_2 peak using ISWT distance. The present study looks to test this formula in a new cohort of patients with IPF.

Arterial oxygen pressure (PaO_2) at the end of a maximal CPET has also been shown to be a significant predictor of survival in patients with IPF (King et al., 2001). This study also investigates the relationship between blood oxygen pressure (PO_2) at the end of a CPET and the end of an ISWT.

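### The section 7.5 regression tests look for a difference, so they cannot by themselves say how similar the new ISWT–VO2 peak relationship is to the earlier formula, and the promised predicted-versus-actual check is not carried into the analysis plan

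*Combined protocol and SAP*

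**What the plan says.** Section 3.1 of the protocol sets a two-part primary objective. The first part is to assess the relationship between VO2 peak and ISWT distance. The second is "to determine how similar it is to a linear relationship from other data collected in a previous study", and the line is then given as VO2 peak = 10.02 + 0.01575 × ISWT distance. The Introduction likewise says the investigators will "compare this with the relationship of the previous study".

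Two other sections describe a check of the formula itself. Section 1.1: "The present study looks to test this formula in a new cohort of patients with IPF". Section 2.2: "It will compare predicted VO_2 peak value with the actual value in a new cohort of patients with IPF".

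Section 7.5 is the whole analysis plan. For VO2 peak it combines the new data with the earlier data, marks them with a study indicator, and continues: "The similarity between the two datasets will be tested using a series of linear regression models". The only other analysis there is a paired t-test on PO2. Neither section 7.5 nor any other section gives the model terms, the estimates to be reported or a criterion for similarity. Predicted-versus-actual VO2 peak is not mentioned in section 7.5.

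**The concern.** There are two gaps.

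The first is a mismatch between question and method. Section 3.1 asks for a degree of similarity. With a study indicator in a regression, what can be tested is whether the study term (a shift in level) or the study-by-distance term (a change in slope) differs from zero. The null hypothesis is no difference. Failing to reject it says little unless the confidence interval is also narrow. Because a series of unspecified models is planned, the choice of terms and of the quantity to rely on also stays open until the data have been seen.

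The second is a promise not carried through. Comparing two fitted lines on pooled data uses the very data that produced the formula. Checking the fixed formula in new patients is a different question, and it is the one that sections 1.1 and 2.2 say will be answered. Two cohorts can share a line while predictions for individual patients are poor.

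At stake is the second half of the primary objective. The first half, whether distance and VO2 peak are related, is not affected.

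**Working it through.** **The plan's own figures.** Section 1.3 gives the sample size: "We aim to recruit a minimum of 43 patients to this study". No alpha, power, effect size or SD accompanies it, so it can be neither reproduced nor called wrong. Section 3.1 gives the intercept 10.02 and slope 0.01575, without standard errors, residual SD or units. The earlier study's size is not stated. What follows therefore illustrates scale.

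**Precision of the slope difference in the pooled model.**

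Inputs: 43 new patients (section 1.3); slope 0.01575 (section 3.1). Assumed: earlier n₂ = 20 to 100; correlation r = 0.6 to 0.8; equal distance SDs and equal residual SDs in the two studies.

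Let b = r/√(1 − r²), the slope in residual SDs per SD of distance. This gives b = 0.750, 0.980 and 1.333 for r = 0.6, 0.7 and 0.8. The 95% CI half-width for the slope difference, as a share of the slope, is

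t(0.975, 39 + n₂) × √(1/42 + 1/(n₂ − 1)) / b.

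- Widest (r = 0.6, n₂ = 20): 2.001 × 0.2765 / 0.750 = 0.74.
- Narrowest (r = 0.8, n₂ = 100): 1.977 × 0.1841 / 1.333 = 0.27.

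| r | n₂ = 20 | 30 | 50 | 100 |
|---|---|---|---|---|
| 0.6 | 74% | 64% | 56% | 49% |
| 0.7 | 56% | 49% | 43% | 37% |
| 0.8 | 41% | 36% | 31% | 27% |

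Multiplied by 0.01575 × 100, the extremes are 1.16 and 0.43 VO2 units per 100 m walked.

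**Would a test notice a halved slope?** Under the same assumptions, with two-sided alpha 5% and a non-central t with non-centrality 0.5 × b / √(1/42 + 1/(n₂ − 1)), the power is about 27% at r = 0.6, n₂ = 20 and about 95% at r = 0.8, n₂ = 100. Over much of the range, a true halving of the slope could well come out non-significant.

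**Sensitivity to the assumptions.** Assume instead a residual SD of 2 to 4 VO2 units, a distance SD of 100 to 150 m and an earlier n of 20 to 80. The half-width is t × (residual SD / distance SD) × √(1/42 + 1/(n₂ − 1)).

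- Widest: 2.001 × (4/100) × 0.2765 = 0.0221, or 141% of 0.01575.
- Narrowest (residual SD 2, distance SD 150 m, n₂ = 80): 0.00504, or 32%.

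**What the promised check would give with 43 patients.** It treats the formula as fixed and needs no earlier n.

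- Mean predicted-minus-actual: half-width t(0.975, 42)/√43 = 2.018/6.557 = 0.31 SD of the errors.
- Each limit of agreement: 2.018 × √(1/43 + 1.96²/84) = 0.53 SD.
- Slope of actual on predicted: half-width t(0.975, 41)/(b√42) = 0.42, 0.32 and 0.23 at r = 0.6, 0.7 and 0.8, where 1 means the formula's slope is right.

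**Same line, poor predictions.** Even if both cohorts share exactly one line, a residual SD of 2 to 4 units (assumed) gives limits of agreement of ±1.96 × 2 = ±3.9 to ±1.96 × 4 = ±7.8 units. A comparison of lines alone would not report this.

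**The case against.** **The regression already contains most of the check.** Predicted VO2 peak is a fixed linear function of distance. So the slope of actual on predicted is the new-cohort slope divided by 0.01575, and the mean error is the gap between formula and new line at the new cohort's mean distance. The spread of the errors follows from the slope and the residual SD. This stands: the gap is one of specification and reporting, and the tool is already named. But section 7.5 does not commit to a fit in the new cohort alone or to reporting these quantities.

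**The harm is conditional.** A reader might infer that the investigators will declare the datasets similar if p exceeds 0.05. The documents do not say so, and the same models can yield estimates with intervals. This stands too. What remains is that section 7.5 speaks of testing similarity and offers no other basis for judging it.

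**Pooling is a reasonable method.** Section 3.1 and the Introduction compare one relationship with another, and a pooled model carries the earlier study's sampling error, which a fixed-formula check ignores. A reader might infer that the fixed-formula check should decide the matter. Nothing in the documents ranks it above the pooled comparison. A rule on mean error alone would also miss a changed slope, since the mean error can be zero when the lines cross at the mean distance.

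**The low end of the formula.** A reader might note that the formula cannot predict below 10.02, while section 1.1 cites a "VO_2 peak of < 8.3 ml/kg/min in a CPET was associated with an increased risk of death", and infer that it fails for the patients who matter most. Section 3.1 states no units, and classifying patients at that level is not an aim of the study. That observation does not support the point made here.

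**Scale of the study.** This is a small single-centre basic science study and a Masters project. That argues for a short fix. It does not remove half of the primary objective.

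**Conclusion.** The concern holds in a limited form and should be fixed. As written, section 7.5 relies on tests for a difference to answer a question about degree of similarity, and it does not carry through the comparison promised in section 2.2. Both findings rest on the text alone.

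The size is illustrative: a half-width of 27% to 74% of the published slope under the main assumptions, and 32% to 141% under the alternative set. The earlier study's n, correlation and SDs are all assumed. The figures show that non-significance could coexist with a materially different slope. They do not show that it will, and they do not show that 43 patients is the wrong number.

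**What to change.** Amend section 7.5 before analysis as follows.

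1. Fit one pre-stated pooled model: VO2 peak on centred distance, study, and study × distance. Keep all terms whatever their p-values. Report the slope difference and the gap between the lines, each with a 95% CI.
2. Add the check of the fixed formula in the new cohort alone. Report mean predicted-minus-actual VO2 peak with 95% CI, limits of agreement, the slope of actual on predicted with 95% CI, and a plot of errors against distance.
3. State that the question of how similar will be answered from these estimates and intervals, and that similarity will not be concluded from a non-significant term. Neither analysis need be ranked above the other.
4. Only if a formal claim of similarity is wanted, have the investigators set tolerances before analysis that cover the slope as well as the average error. Otherwise report estimates and intervals.

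The cost is protocol wording and a little more analysis on data already to be collected. The downside is that, with the precision shown above, the answer on similarity may be inconclusive.
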